4 STUDY SETTING

 The single-centre study will be conducted at the Manchester Foundation Trust, Wythenshawe Hospital site. Patients will be identified from our annual waiting list register at the cardiac waiting list office.

5 SAMPLE AND RECRUITMENT

This pilot study will have a randomised design and will be a single-centre trial with 2 arms, including one experimental immersive head mounted VR group and one control group.

They will be randomly allocated:

- 1. Control group: Normal routine care with 15 minutes music session with WorWoder Wireless blue tooth headset.
- 2. Virtual reality (VR): Normal routine care and 3D landscape images with guided mindfulness for 15 minutes session with VR headset.
- 3. Please note that we will be recruiting patients who are undergoing surgery in the morning and afternoon. This may alter the cortisol levels of the patient, but this will be taken into consideration while comparison analysis.

Control group: Normal routine care

Control group patients will receive normal preoperative surgical admission processes which includes admission to the hospital by the administration/nursing team, meeting with surgical core trainees to complete preoperative details and informed consent. Patients may also receive an experiential talk about the surgery pathway given by Ticker Club (heart charity) volunteers; this is an ad hock service. Full surgical pre, intra and postoperative booklet will be provided to the patient by the preoperative outpatient nurses. As a control, we will be asking the control group patients to listen to music of their choice for 15 minutes music session with WorWoder Wireless blue tooth headset.

Session one pre surgery: They will be asked to listen to the music for 15 minutes within one hour time period of their surgery.

Session two: They will be asked to listen to the music post-surgery on day 3 (around 6pm).

Intervention arm: VR

Intervention group patients will receive the same pre-operative preparation as the control group with the addition of three Virtual Reality (VR) sessions using a head-mounted 3D display. This 15 minute long immersive VR experience from Rescape Innovations (https://www.rescape.health/) features the visualisation of 10 beautiful environments and landscapes (Figure 1). It provides the viewer two guided mindfulness sessions which teach breathing and relaxation techniques and is accompanied by the sounds of nature and soothing guidance. In between the two mindfulness sessions lies a montage of natural environments to enjoy whilst calmly relaxing and escaping to these peaceful surroundings. Participants are not required to interact with this experience; they simply relax during the session.

Patients will be instructed to discontinue use if they experienced any discomfort or side effects (dizziness, motion sickness, etc); this will be recorded as a side effect and limitation of the therapy. Participants will be instructed to refrain from engaging in other video game activities, watching television, or using their phones during the time of intervention to standardise the impact of their assigned intervention.

Session one: Patient will receive the VR session pre surgery within one hour time period of their surgery. Session two: They will receive the VR session on day 3 post surgery (around 6pm).

Hygiene measures:

Two VR headsets (£6000) and two WorWoder Wireless blue tooth headset (£100) will be provided by the company free of cost for this study and it will be used within the hospital premises. Infection control measures will be used as per manufacturer recommendation. Adequate hand hygiene is required upon

handling the device or the controllers. Adequate disinfection of the device between each patient use, includes dismantling of all separable parts and thorough disinfection with non-alcoholic cleaners as per manufacturer's recommendation.

Patients who might not adequately understand verbal explanation or written information given in English will be provided with hospital interpreters. All the patients whose first language is not English will have an interpreter booked by the hospital.

Eligibility criteria are as follows:

All adult cardiac surgery patients will be considered for inclusion in this study regardless of age, disability, gender reassignment, marriage and civil partnership, pregnancy and maternity, race, religion and belief, sex, and sexual orientation except where the study inclusion and exclusion criteria EXPLICITLY state otherwise.

Inclusion criteria:

- Adults undergoing first time elective cardiac surgery (coronary artery bypass surgery and aortic/mitral valve surgeries), age more than 18 years, who will give informed consent for their participation to this study.
- Urgent in patient who are well enough to read and understand the study and patient information leaflet.

Exclusion criteria:

- Psychiatric antecedents, claustrophobia or acrophobia, diagnosis or self-reported anxiety disorder, hearing or visual impairment, Infectious cases (example: conjunctivitis), redo surgery, critical preoperative state, impaired cognitive function, current diagnosis of epilepsy, dementia, or other neurologic disease, receipt of anxiolytic drugs or sedatives within the preceding 24 hours, or injury to the face, or non-infectious, infectious skin conditions that would prevent comfortable use of the VR hardware.
- Patient who are having complex cardiac surgeries.
- Patient who are admitted for an emergency cardiac surgery.
- Patients who do not want to listen to music on their bedside Bluetooth enabled headphones.
- Patient who does not want to wear VR headsets.

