6 DATA COLLECTION AND DATA ANALYIS

6.1 Data Collection

Patient data: Generic

- All preoperative clinical data of patient demographics will be obtained from the patients' clinical notes, clinical database, laboratory reports.
- The STAI and cortisol outcomes will be measured for this study at 4 time points pre- and postsurgery.

Clinical patient data:

All clinical data will be collected by research team members.

All the clinical data will be collected prospectively into a relational database. General demographics including age, sex, race, body mass index, hospital admission.

Data collection: Please note that the questionnaires, STAI, (Table 1) will be applicable to both study arms.

Demographic factors

All basic pre and post operative variables will be collected such as on age and gender, duration of the surgery, medications, consumption of alcohol, tobacco and type of cardiac surgery. Alcohol and tobacco consumption will be recorded as withdrawal symptoms could also influence the participant's behaviour postoperatively.

Time points of collecting anxiety STAI scores and cortisol assay:

Control/VR intervention group:

The first and second set of STAI questionnaire and cortisol assay swab will be collected before and after the control/VR session within 30 minutes after the control/intervention. The third and fourth set of STAI questionnaire and cortisol swab will be collected on day 3 post-surgery around 6 pm before and after the control/VR session within 30 minutes.

Physiological variable

We will record heart rate, blood pressure and respiratory rate at baseline (pre-surgery), before and after the VR intervention, post-surgery to assess the changes and compare between the two groups. We will record same physiological assessment for the control group before and post-surgery. The time period of the assessment will be matched as similar as possible to reduce any bias.

Psychological variable

State-Trait Anxiety Inventory (STAI) will be used to measure patients' self-evaluation stress and anxiety. It is a set of 20 statements with scores 1 to 4 which people have used to describe how they feel "at this moment."

It will be collected pre- and post-surgery and at the same time points for both groups to assess any difference in anxiety between groups.

In addition,

- VR experience for pre- and post-surgery.

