6.3 Planned Statistical analyses: Clinical

Analyses will be mainly descriptive. Any test will be for exploratory and for hypothesis generating purposes. Proportion of consent and dropouts and their 95% CI will be reported. Demographics, baseline, physiological and medical characteristics will be summarised for the whole cohort and for each arm separately. Summary statistics of anxiety and stress score and cortisol levels will be provided at each time point (baseline and day 3 post operatively) for each arm.

Number of patients approached and proportion consenting to participate will be reported.

Number and percentage of patients removed due to ventilation will be reported.

Number and percentages of patients not completing VR session for any reason will be reported.

Pre and post operation anxiety scores will be compared between the two groups using t-test or equivalent non-parametric test. Pre and post operation cortisol levels will be compared between the two groups using t-test or equivalent non-parametric test. Changes in stress scores and cortisol levels will be assessed. Pre and post operation cortisol levels and anxiety scores will be correlated for all and for each arm separately.

Result from VR experience and VR absorption for the intervention group will be summarise.

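### Pre-surgery cortisol follows the surgery slot, and section 6.3 does not carry out the protocol's promise to allow for it; between arms the cost is noise and chance imbalance, not bias

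*Protocol*

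**What the plan says.** Section 5 of the protocol states that "we will be recruiting patients who are undergoing surgery in the morning and afternoon" and continues: "This may alter the cortisol levels of the patient, but this will be taken into consideration while comparison analysis".

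The same section ties the first session to the operation in both arms. For controls, "They will be asked to listen to the music for 15 minutes within one hour time period of their surgery"; for the VR arm, "Patient will receive the VR session pre surgery within one hour time period of their surgery". The clock time of the pre-surgery swabs therefore follows the surgery slot. Section 6.1 fixes the later swabs for everyone: the third and fourth sets "will be collected on day 3 post-surgery around 6 pm before and after the control/VR session within 30 minutes".

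Section 6.3 gives the analysis in three sentences. For the contrast of the arms it has "Pre and post operation cortisol levels will be compared between the two groups using t-test or equivalent non-parametric test". On change over time it says no more than "Changes in stress scores and cortisol levels will be assessed". For the link with STAI it has "Pre and post operation cortisol levels and anxiety scores will be correlated for all and for each arm separately". It names no covariate, stratum or sampling time, and it does not say how the before-session and after-session swabs of one session are to be used together. The section also describes the analyses as mainly descriptive and any test as exploratory. Section 3 lists cortisol as a secondary outcome and its correlation with STAI as a secondary objective.

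**The concern.** The protocol identifies a source of variation in cortisol and undertakes to deal with it, but the section that defines the comparison names methods that, as written, do not. Three quantities are exposed:

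- the pre-surgery cortisol level, sampled in the morning for some patients and the afternoon for others;
- the change from pre-surgery to day 3, which compares a slot-dependent time with about 6 pm, so the clock shift differs between morning and afternoon patients;
- the correlation of cortisol with STAI wherever pre-surgery cortisol enters.

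At stake are precision in a small trial, a chance slot imbalance that nobody adjusts for, a diluted correlation, and a before-and-after change that could be misread as a response to surgery or to VR. The plan collects a before-session swab that would remove much of this, yet section 6.3 gives it no stated role.

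**Working it through.** **The plan's own figures.** The protocol gives no figure on time of day. Its related figures reproduce: 30/(1 − 0.10) = 33.3, rounded up to 34 enrolled (section 6.2), and 4 × 30 = 120 swabs (section 6.1).

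**Inputs.** From the protocol: 15 per arm, random equal allocation, no stratification by slot stated, session 1 within an hour of surgery, session 2 around 6 pm on day 3. Assumed, because the protocol gives none of them: half of patients are morning cases; morning/afternoon cortisol ratio 1.5, 2 or 3; within-slot SD of log cortisol 0.5.

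**1. Chance imbalance of slot.** If exactly 15 of the 30 are morning cases, the number in one arm is hypergeometric (30, 15, 15), and the arms differ by 3 or more with probability 0.466 and by 5 or more with probability 0.143. If instead each patient is independently a morning case with probability 0.5, the first figure is 0.36 and the second 0.10; with 70% morning cases they are 0.32 and 0.07.

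**2. Size of the shift against its standard error.** For a difference of k morning patients, the log-scale shift is ln(ratio) × k/15. The unadjusted variance is 0.5² + 0.25 × ln(ratio)², and the standard error is √(2 × variance/15).

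| Ratio | Variance inflation | SE (log) | Shift, k = 3 | As % | Shift/SE |
|---|---|---|---|---|---|
| 1.5 | 1.16 | 0.197 | 0.081 | 8% | 0.41 |
| 2 | 1.48 | 0.222 | 0.139 | 15% | 0.62 |
| 3 | 2.21 | 0.271 | 0.220 | 25% | 0.81 |

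A difference of 3 stays under one standard error throughout. A difference of 5 gives shifts of 0.135, 0.231 and 0.366, which are 0.69, 1.04 and 1.35 standard errors.

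**3. Error rate and precision of the pre-surgery comparison.** Here the slot shift is expressed as 0.5, 1.0 or 1.5 within-slot SDs (a ratio of 1.5 at log SD 0.5 is 0.405/0.5 = 0.81 SD). In 20,000 simulated trials with no treatment effect and half morning cases, the unadjusted t-test rejected in 5.0% to 5.3% at each shift. The SD rises by the factor √(1 + 0.25 × shift²): 3%, 12% and 25%. The equivalent sample is 15/(1 + 0.25 × shift²) = 14.1, 12.0 and 9.6 per arm. For an assumed true difference of 1 SD at two-sided 0.05, power is 76%, 69% and 59% unadjusted, against about 78% with slot adjusted for (normal approximation, ignoring the lost degree of freedom).

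**4. Day-3 comparison between arms.** Both arms are swabbed around 6 pm, so slot does not enter. Simulated SD is 1.00 and the error rate about 5%.

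**5. Before-to-after change within a session.** Slot cancels if its effect is constant over the session. With an assumed within-session correlation of 0.9, the SD of the change is 0.45 at every shift.

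**6. Pre-surgery to day-3 change.** With no true change, the mean moves by −0.5 × shift = −0.25, −0.50 and −0.75 SD. The difference between arms in this change remains unbiased but is noisier: its SD is 1.03, 1.12 and 1.25 instead of 1.00, with an assumed pre-to-post correlation of 0.5.

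**7. Pre-surgery cortisol–STAI correlation.** An assumed true correlation of 0.40 becomes 0.38, 0.35 and 0.31.

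**The case against.** The strongest reply is that section 5 already commits the trial to considering slot, that section 6.3 is a short outline, and that a covariate or stratum is the sort of detail a protocol leaves to the SAP. Section 6.3 does not rule adjustment out, and the SAP is not shown. This stands in part: nobody can say from the protocol that the promise will be broken. What remains is that the named methods make no use of slot or of the before-session swab, and a better method is available at almost no cost. Nor can one say that swab times go unrecorded: the case report form is not shown, and the list of variables in section 6.1 is open-ended. That list simply does not require them.

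Three stronger readings are tempting, and the documents do not support them.

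- A reader might infer that every cortisol result is mixed with time of day. It is not: the day-3 swabs share a clock time across arms, and within-session changes largely cancel it.
- A reader might infer that slot imbalance would pass for a VR effect. Randomisation prevents systematic bias, the error rate stays near 5%, and the t-test's own standard error already includes the slot spread.
- A reader might infer that the STAI correlation would reflect clock time instead of stress. Under the assumptions above it is diluted, not replaced.

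It is also fair that the protocol says only that changes will be assessed. It does not say that the change to day 3 will be read as an effect, so the caution on that point is preventive.

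**Conclusion.** The point holds in limited form. Pre-surgery cortisol levels, their change to day 3 and their correlation with STAI carry time-of-day variation that the protocol recognises and that the methods named in section 6.3 leave in place. For the comparison between arms, the consequence is lost precision (14.1 to 9.6 effective patients per arm instead of 15) and a fair chance of slot imbalance, of modest size at a difference of 3. Only the within-patient change from pre-surgery to day 3 has its mean displaced. These sizes rest on an assumed morning share, morning/afternoon contrast, SD and correlations, none of which the protocol gives. Weight is low to moderate, because cortisol is a secondary outcome, every test is exploratory and an SAP may supply the method.

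**What to change.** In section 6.3 (or in the SAP, with a cross-reference from section 5):

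- **Session 1:** compare arms by ANCOVA of log after-session cortisol on arm, log before-session cortisol and surgery slot (AM/PM).
- **Session 2:** use the same model without slot.
- **Sampling time:** record the clock time of every swab.
- **Correlation with STAI:** report it by session, adjusted or stratified for slot before surgery. This keeps the stated secondary objective. Add correlations of within-session changes as a supplement.
- **Interpretation:** state that the within-patient change in cortisol from pre-surgery to day 3 will not be interpreted as a stress or VR effect.

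The cost is one time field on the case report form, a few sentences in section 6.3 and one degree of freedom for slot in the session 1 model. The before-session swab is already collected, and no session, visit or sample size changes.

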In addition, we will explore if there is association between salivary cortisol levels as a potential biomarker for stress and self-completed questionnaires anxiety level (STAI). We will obtain four samples of before and after control/VR intervention pre- and post-surgery to see the co-relation.

Expected outcomes:

This study will identify whether the use of VR technology has the potential impact to reduce pre and post operative anxiety and stress.

2. Research Question

- 1. Can immersive head mounted Virtual Reality headset intervention reduce pre-and postoperative anxiety and stress in adult patients undergoing elective cardiac surgery?
- 2. Is the use of VR technology being feasible immediate post-surgery on cardiac surgery patients?

3 Objectives and Outcomes assessments

2.1 Primary Objectives:

Assessment of anxiety, stress levels between two groups

2.2 Secondary Objectives:

- Feasibility of VR technology.
- Correlation between cortisol level and STAI
- VR experience
- VR absorption

2.3 Outcome Measures:

- **Primary outcome:** patients' anxiety and stress levels four time points (before and after each session on pre- and post-surgery (STAI)
- Secondary outcomes:
- Cortisol swabs four time points (before & after each session on pre- and post-surgery).
- Physiological parameters pre- and post-surgery.

For intervention group only:

- Patient experience about VR (Rescape™ company questionnaire))
- VR Absorption and immersion scale (VAS 0-10)
- Proportion of patients consenting to VR.
- Proportion of patients completing the VR sessions.
- Adverse events due to VR.

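### The proportion consenting to VR is an intervention-arm outcome in patients already selected for willingness, so it is about 100% by construction, and section 6.3 leaves open whether refusers are counted

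*Protocol*

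**What the plan says.** Four parts of the protocol bear on this point.

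- **Objective and outcome (sections 2.2 and 2.3).** "Feasibility of VR technology" is a secondary objective. One of the measures that bear on it is "Proportion of patients consenting to VR", placed under the subheading "For intervention group only". No numerator or denominator is given. Completion of the VR sessions is a separate item in the same list.
- **Eligibility (section 5).** The exclusion criteria include "Patient who does not want to wear VR headsets" and "Patients who do not want to listen to music on their bedside Bluetooth enabled headphones". The inclusion criterion for elective patients covers those "who will give informed consent for their participation to this study".
- **Recruitment and consent (sections 5.1 and 5.2).** Section 5.1 says that eligible patients are informed about the study. Section 5.2 has written and verbal consent taken on admission, 24 hours before surgery, and does not limit this to elective patients.
- **Analysis (section 6.3).** "Number of patients approached and proportion consenting to participate will be reported", and also "Proportion of consent and dropouts and their 95% CI will be reported". Non-completion of VR sessions for any reason is reported separately.

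**The concern.** An uptake measure has to be taken in people who could have said no. As listed, this one is taken in the VR arm, which patients reach only after agreeing to the study and after anyone unwilling to wear the headset has been excluded. The outcome is then a condition of entry.

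The section 6.3 consent proportion could fill the gap, but two features weaken it. It concerns consent to the study as a whole (allocation to VR or music, saliva swabs, questionnaires), not to VR. And because unwillingness is written as an exclusion, the same refusal can be logged either as approached and declined or as ineligible.

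The analyses are mainly descriptive, so feasibility proportions are among the main products of this pilot, and willingness to use VR is something a larger trial would need to know. Refusals logged as ineligibility cannot reliably be recovered later.

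**Working it through.** **Inputs from the protocol.** 15 patients per arm, 30 in total, raised to 34 for 10% dropout (section 6.2); equal allocation (Abstract, Methods). Check of the stated total: 30 / (1 − 0.10) = 33.3, rounded up to 34, which agrees. Equal allocation gives 34 / 2 = 17 per arm. The protocol gives no expected number approached, refusal count or uptake rate.

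**Step 1: the outcome as listed.** All n patients in the VR arm have consented and none has met the headset exclusion, so the proportion is n/n. When x = n, the exact (Clopper-Pearson) 95% lower limit is 0.025^(1/n).

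- n = 15: 15/15 = 100%, lower limit 0.025^(1/15) = 0.782, CI 78.2 to 100%.
- n = 17: 17/17 = 100%, lower limit 0.025^(1/17) = 0.805, CI 80.5 to 100%.

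The interval looks like sampling information but carries none about willingness, because the value is set by the entry rules.

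**Step 2: the section 6.3 consent proportion under the two possible denominators.** All counts except the 34 enrolled are assumptions: 10 patients decline for other reasons, v decline because of VR, m because of music.

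- Refusers counted: 34 / (34 + 10 + v + m).
- Refusers classed as ineligible: 34 / (34 + 10) = 34/44 = 77.3% (95% CI 62.2 to 88.5), whatever v and m are.

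| v | m | Approached | Consent, refusers counted (95% CI) | Consent, refusers ineligible | Declining because of VR (95% CI) |
|---|---|---|---|---|---|
| 5 | 2 | 51 | 34/51 = 66.7% (52.1 to 79.2) | 77.3% | 5/51 = 9.8% (3.3 to 21.4) |
| 15 | 5 | 64 | 34/64 = 53.1% (40.2 to 65.7) | 77.3% | 15/64 = 23.4% (13.8 to 35.7) |
| 30 | 5 | 79 | 34/79 = 43.0% (31.9 to 54.7) | 77.3% | 30/79 = 38.0% (27.3 to 49.6) |

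If refusers are counted, consent falls as refusals rise. If they are classed as ineligible, it does not respond to refusal of VR at all. The last column is what a pilot of VR acceptability would want, and no outcome in the protocol, as worded, gives it.

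**Step 3: does the text choose a denominator?** Section 6.3 speaks of patients approached, which suggests that refusers count. Section 5 makes refusal an ineligibility, and section 5.1 speaks of informing eligible patients, which suggests that they do not. Yet willingness can normally be judged only after the patient has been told about VR and music. The passages leave both readings open.

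**The case against.** **Section 6.3 already provides an uptake estimate.** A reader might infer that every uptake figure in this protocol is forced to 100%. The documents do not support that: section 6.3 plans the number approached and a consent proportion with a 95% CI, and neither is fixed. The statement about 100% applies only to the intervention-arm outcome in section 2.3.

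**Nothing says that refusers leave the section 6.3 denominator.** A reader might infer that they do. No passage states this, and a patient who refuses after being informed has in the ordinary sense been approached. What stands is an ambiguity, not a stated exclusion.

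**A VR-arm patient can still refuse on the day.** Consent precedes the first session, withdrawal is allowed at any time (section 5.2), and refusal of day 3 follow-up is foreseen (section 8.1). That is true, but reading the outcome as agreement at the bedside largely repeats the separate completion outcome and the reporting of non-completion.

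**Requiring willingness to accept either arm is ordinary in a randomised trial.** Also true, and the proposed change would not alter who is enrolled. Consent already keeps unwilling patients out, so the two exclusion items add no protection.

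**The reasons may be logged anyway.** Headset and music refusal are separate criteria, so a log kept by criterion could tell them apart. The log, the data management plan and any SAP were not available for this review, so it cannot be said that the reasons will be lost. But the eligibility criteria and the placement of the outcome are protocol statements.

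**Feasibility does not rest on this one measure.** Completion, adverse events, VR experience and removal for ventilation also bear on feasibility after surgery, and the entry rules do not fix them, although they are observed in patients willing to use VR. This limits the weight of the point without removing it.

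**Conclusion.** The point holds in a limited form. The section 2.3 outcome on consenting to VR will be about 100% by construction and cannot inform acceptability. This follows from the protocol's own entry rules and needs no assumption beyond reading the intervention-only placement as written.

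The section 6.3 consent proportion is informative in principle, but it concerns the whole study and its treatment of refusers is unresolved. In the assumed scenarios the two treatments differ by about 11 percentage points (77.3 − 66.7 = 10.6) with few refusals and about 34 (77.3 − 43.0 = 34.3) with many. These sizes depend entirely on assumed counts and illustrate how much the choice could matter; they do not predict this trial's refusal rate.

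The anxiety comparison, the cortisol analyses and safety reporting are unaffected. The change is worth making because it costs almost nothing and turns a stated feasibility outcome into an informative one.

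**What to change.** 1. In section 2.3, take the consent-to-VR item out of the intervention-only list.
2. In section 5, remove the two unwillingness items from the exclusion criteria and record unwillingness to use VR or to listen to music as a reason for declining on the screening log.
3. In section 6.3, define the denominator as all otherwise-eligible patients approached. Report over it, each with a 95% CI, the proportion consenting to the study, the share declining because of VR and the share declining because of music.
4. Keep session completion, with all patients randomised to VR as denominator, as the arm-specific measure.

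The cost is protocol wording, one screening-log field and a reported consent rate that may be lower. The log field should be in place before screening starts; if screening has begun, it should be added from that date and earlier refusals recoded where the records allow.
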